7.6 Baseline data

- Patient details (e.g. name, NHS number, date of birth, sex)
- COVID-19 symptom onset date
- COVID-19 severity (appendix 2)
- Date positive SARs-CoV2 test
- Major comorbidity/ Medical History (e.g. heart disease, diabetes, chronic lung disease)
- Regular medications
- Duration symptoms and type of symptoms
- Wellbeing VAS Score
- Demographics
- Smoking Status
- Vaccinated against COVID-19? Dates? And which vaccine?

7.7 Trial assessments

Trial Visit Schedule								
	Screening	Day 1	Day 3 (+/-1)	Day 7 (+/-1)	Day 10 (+/-1)	Day 14 (+/-1)	Day 28 (+/-1)	Early Exit
Verbal Consent	X							
Eligibility	X							
Inclusion/Exclusion	X							
Demographics	X							
Medical History	X							
Duration of Symptoms	X							
Symptom Check	X	X	X	X	X	X	X	X
Comorbidities	X							
Concomitant Medications	X	X	X	X	X	X	X	X
Smoking Status	X							
Electronic Consent (telephone consent if electronic not possible)		X						
Written Consent (if electronic consent not possible)						X		
Randomisation		X						
Dispense Trial Liquid		X						
Adverse Events			X	X	X	X	X	X
Telephone/Emails Visit			X	X	X	X	X	X
Trial Liquid Compliance			X	X	X	X	X	X
Wellbeing VAS Score		X	X	X	X	X	X	X

BERRY Protocol v 6.2 22.07.2021 IRAS 282732

7.8 Long term follow-up assessments

With the exception of any pregnancy outcomes, Data collection will end at day 28 following randomisation. Research team will follow up the outcomes of any notified pregnancies.

This will be to check to see if patients have been admitted to hospital in the 28 days following a positive SARS-CoV2 test.

If admitted:

- Date of hospitalisation
- Admission hospital and location (i.e. HDU/ITU) – reason and outcome. Date discharge / death

7.9 Qualitative assessments

N/A

7.10 Withdrawal criteria

Subject withdrawal criteria

- Patient choice (no justification required)
- Responsible physician choice - medical reasons (i.e. individual adverse events or new information gained about a treatment).

Patients may withdraw their consent to participate in the trial at any time without reason. No further trial procedures will be undertaken and no data or samples will be collected from the time of withdrawal.

However, data collected up to the time of consent withdrawal will be included in the data reported for the trial. The Investigator should inform the coordination team as soon as possible and complete the consent withdrawal Case Report Form (CRF).

Circumstances where the trial may be prematurely stopped include:

- Failure to recruit participants at the required rate to meet target.
- Publication of trial results for an alternative to Sambucol which shows dramatic improvement in symptoms when given pre-admission.
- Identification of a serious safety issue
- Sponsors request

7.11 Storage and analysis of clinical samples

Not applicable – No clinical or biological samples.

7.12 End of trial

The trial end date - 01/11/2022

Last patient last visit date – 01/10/2022

8 TRIAL TREATMENTS

8.1 Name and description of treatments

Sambucol® Black Elderberry Original (Sambucus nigra) Liquid

Constituents: 29.4 % (w/w) Black Elderberry (Sambucus nigra) fruit juice, 70% (w/w) of glucose syrup.

The main ingredient is black elderberry juice and it meets the requirements of the Directive

BERRY Protocol v 6.2 22.07.2021 IRAS 282732

2012/12/EU relating to fruit juices. The product also contains two food additives: citric acid (E330) as acidity regulator and potassium sorbate (E202) as preservative.

Primary packaging: Plastic PET amber bottles 120ml. Caps are PP28 white tamper-proof caps with security seal.

Secondary Packaging: None. Outer Carton: Cardboard 376mm x 191mm x 116mm. 32 bottles per case.

Placebo for Sambucol® Black Elderberry Original (Sambucus nigra) 120ml

Constituents: 70% (w/w) of glucose syrup, Flavouring agent: Elderberry Blossom. Colourants: Eurocert Carmoisine (311804) (E-122) and Eurocert Brilliant Black PN (419358) E-151. The product also contains two food additives: citric acid (E330) as acidity regulator and potassium sorbate (E202) as preservative.

Primary packaging: Plastic PET amber bottles 120ml. Caps are PP28 white tamper-proof caps with security seal.

Secondary Packaging: None. Outer Carton: Cardboard 376mm x 191mm x 116mm. 32 bottles per case.

8.2 Regulatory status of the treatment

Sambucol Liquid is marketed within the EU and other countries as a food supplement.

8.3 Product Characteristics

Sambucol® Black Elderberry Original (Sambucus nigra) Liquid has been used as a supplement since 1991 with no reports of adverse effects received by the Manufacturer.

8.4 Treatment storage and supply

8.4.1 Storage: Sambucol/placebo will be stored at ambient temperature, below 25°C there are no temperature monitoring requirements needed.

8.4.2 Shipment: Treatments will be supplied Free of Charge by Pharmacare (Europe) Limited.

8.4.3 Ordering and Re-Ordering: Initial shipment will be shipped to site following site activation. Further supplies – logistics as agreed between site and Pharmacare.

8.4.4 Receipt: Shipments will be received by Pharmacy Clinical Trial Staff and inspected for any damage or defects. In the event of product defect or damage contact [contact] and cc. [contact]

8.4.5 Accountability: Pharmacy will keep an inventory log for stock received. The Batch number will be recorded in the CRF of product issued to each participant. No other accountability records will be kept.

8.4.6 Dispensing: On confirmation of eligibility, e consent and randomisation will occur. Patients will be randomised to active or placebo liquid and a 14 day supply of study liquid dispensed The Research Nurse will write the Patient's Trial ID No. on the label and record the Batch number in the patient's record The liquid can either be collected by a family member or friend and dropped to the patient's doorstep – or the research team will drop to the doorstep so that everyone has a chance to take part. If a participant lives further away the liquid will be delivered to their home address by courier

8.4.7 Recall Procedure: In the event of a product defect participants will be telephoned and asked to stop taking the product and either to destroy as for household waste or to return any unused product

to site according to the seriousness of the defect. Further investigation will be by Pharmacare's Recall Procedure, as appropriate.

BERRY Protocol v 6.2 22.07.2021 IRAS 282732

8.4.8 Post-trial access to Sambucol Liquid: Various Sambucol® products are readily available to purchase from Health Food stores, Pharmacies and various on-line retailers. Sambucol will not be supplied to participants after the end of the trial.

Blinding: Active Sambucol and Placebo will be packaged and labelled as THE BERRY TRIAL LIQUID. The active and placebo packs will be differentiated by – Q and Z respectively appended to the Batch Number. Packs will be received and stored by unblinded Pharmacy Staff and personnel distributing treatments to participants will also be unblinded.

8.5 Preparation and labelling of Treatments

Active Sambucol and placebo will be packaged and labelled as 'THE BERRY TRIAL LIQUID' and supplied by the Manufacturer details of dosage and storage conditions, Batch Number and expiry date; PI Name; Trial name; space for Pt Trial ID no and 'For Clinical trial Use only' as shown in Appendix 1.

Sponsor Name, address and contact telephone number will be provided on the Patient Information Leaflet.

8.6 Dosage schedules

All participants will take a fixed dosage of 15ml orally four times a day. Total daily dose 60ml. Missed doses can be taken at any time. If the patient vomits shortly after taking a dose they can repeat the dose.

8.7 Dosage modifications

There are no dose modifications. If a participant feels unwell after taking a dose they should contact the Research Nurse to discuss whether they should continue or stop treatment and withdraw from the trial. Research Nurse will seek advice from the Chief Investigator.

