9.7 Overdose

Participants will be advised in the PIS to contact the research team on for advice if they believe they have taken too much Sambucol/Placebo or an overdose. Participants will also be asked about their compliance with the recommended dosage during telephone consultations with the Research Staff. Emergency contact for 24hr

Overdose definition: More than 50 % excess dosage (> 90ml) in any 24 hour period. Identified during participant consultations. In the event of a confirmed overdose the participant will be withdrawn from the trial.

Any overdose event will be recorded as a protocol deviation and reported to the Sponsor.

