10.3.2 Primary outcome analysis

The primary outcome, VAS symptoms score at 10 days, will be analysed using Analysis of Covariance (ANCOVA). The scores at 10 days will be used as the outcome variable, with the symptom scores at baseline included as a covariate.

The primary analysis will be performed on an Intention to Treat (ITT) basis. Participants will be analysed in the arm to which they were randomised, irrespective of whether they received their allocated treatment.

If the population varies for the ITT analysis, a per protocol analysis will be performed, as a sensitivity analysis.

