10.7 Participant population

The primary analyses for all analysis (primary, secondary, safety) will be done on an ITT basis, with patients included in the groups to which they were randomised, irrespective of whether they received their allocated treatment.

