10.8 Procedure(s) to account for missing or spurious data

Spurious data will be identified and checked with original source documentation. If found to still be spurious, based on clinical values may be excluded from the analysis. Any omissions will be noted and justified.

Patients with missing data for any given variable will be omitted from the analysis. No imputations of missing data will be performed.

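### Sections 8.7 and 9.7 link stopping the liquid to leaving the trial, so exits before day 9 leave no day-10 VAS for the ITT analysis

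*Combined protocol and SAP*

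**What the plan says.** Section 8.7 has a participant who feels unwell after a dose contact the Research Nurse to "discuss whether they should continue or stop treatment and withdraw from the trial"; the nurse takes advice from the Chief Investigator. Section 9.7 defines overdose as more than 90 ml in 24 hours and states: "In the event of a confirmed overdose the participant will be withdrawn from the trial".

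Section 7.10 lists "Responsible physician choice - medical reasons" as a ground for withdrawal and gives no follow-up rule for it. Its only rule on later data is "No further trial procedures will be undertaken and no data or samples will be collected from the time of withdrawal", which sits in the paragraph on withdrawal of consent. Overdose is not listed there.

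The schedule in section 7.7 includes the "Wellbeing VAS Score" at day 10 (plus or minus 1 day) and at Early Exit. The primary analysis (10.3.2) is an ANCOVA of the day-10 score on the ITT principle: "Participants will be analysed in the arm to which they were randomised, irrespective of whether they received their allocated treatment". Section 10.7 extends the same principle to all analyses. Section 10.8 adds: "Patients with missing data for any given variable will be omitted from the analysis. No imputations of missing data will be performed".

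**The concern.** An analysis that disregards treatment received needs outcomes from people who have stopped treatment. Sections 8.7 and 9.7 treat stopping the liquid and leaving the trial as one step, so those outcomes may never be collected.

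The 8.7 route matters more. Its trigger is feeling unwell and the outcome is a wellness score, so the missing scores are plausibly related to what they would have been. The 9.7 loss is not obviously related to outcome.

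If early leavers were less well and more numerous in one arm, that arm's observed mean would be too high. Without such a difference between arms, the only cost is precision. Scores not collected cannot be recovered by the full SAP that section 10.3 says is still to come.

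**Working it through.** **Text, side by side**

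- *Options offered.* 8.7: continue, or stop and leave. 9.7: leave. Stopping the liquid while staying in follow-up appears in neither.
- *Follow-up after exit.* 7.10 ends data collection on withdrawal of consent. For physician-led and overdose exits, follow-up is not stated, which is different from forbidden. Sections 9.9 and 13.11 follow adverse events, not the VAS.
- *Early Exit score.* The day-10 window is days 9 to 11, so an Early Exit VAS can serve as the day-10 score only for an exit on day 9 or later.
- *Analysis.* With no day-10 score, 10.8 omits the participant.
- *Routes that do not cause this loss.* Missed doses do not end participation (8.6), admitted participants continue the liquid (8.9), and death is scored 0 (section 7 table).
- *Overdose line.* 6 × 15 = 90 ml does not exceed the limit; 7 × 15 = 105 ml does. Section 8.6 puts no time limit on making up missed doses, so read literally, four scheduled plus three made-up doses in 24 hours would follow 8.6 and trigger 9.7.

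**The plan's own sample size (10.1)**

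Inputs: SD 20, difference 10, 5% significance level (two-sided assumed), 90% power. The two-sample t-test calculation with standardised difference 10/20 = 0.5 gives 85.03, rounded up to 86 per group, 172 in total. Allowing for 15% dropout, 86/0.85 = 101.2, rounded up to 102 per group, or 204. The stated figures reproduce. The allowance is 204 − 172 = 32 losses.

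**Bias from omission**

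Let p be the share of an arm lost and g the amount by which leavers' unseen day-10 VAS falls below that of stayers. The observed arm mean is too high by p × g, so

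bias = p(active) × g(active) − p(placebo) × g(placebo),

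which is (difference in p) × g when the gap is equal. Under ANCOVA, g is the residual gap: raw gap − slope × baseline gap. The documents give neither p nor g, so the values below are assumptions, with slope 0.5.

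| Loss in the two arms | Raw gap | Baseline gap | Formula | Bias (units) | Simulated |
|---|---|---|---|---|---|
| 5% vs 5% | 20 | 0 | 0 × 20 | 0 | −0.02 |
| 7% vs 5% | 20 | 0 | 0.02 × 20 | 0.4 | 0.41 |
| 7% vs 5% | 20 | 20 | 0.02 × (20 − 10) | 0.2 | 0.20 |
| 10% vs 5% | 20 | 0 | 0.05 × 20 | 1.0 | 0.99 |
| 10% vs 5% | 20 | 20 | 0.05 × (20 − 10) | 0.5 | 0.47 |
| 15% vs 5% | 30 | 0 | 0.10 × 30 | 3.0 | 3.01 |

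The simulated column is complete-case minus full-data ANCOVA, with 102 per arm, SD 20, slope 0.5 and 4000 runs. Of 102 per arm, a 2-point difference is about 2 people and a 5-point difference about 5.

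The last row is an extreme case. It needs 0.15 × 102 + 0.05 × 102 = 20.4, about 20 early exits by these routes out of the 32 losses allowed for all causes, and is not expected.

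**Scale and precision**

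Unadjusted SE at 86 per arm: 20 × √(2/86) = 3.05. A bias of 1.0 unit is 1.0/3.05 = 0.33 SE and 10% of the 10-unit target.

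If five more per arm were lost beyond the allowance (86 to 81), the SE would be 20 × √(2/81) = 3.14, and two-sided 5% t-test power for 10 units would fall from 0.903 to 0.885.

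**The case against.** The strongest reply is that the plan is silent rather than contradictory. The sentence ending data collection concerns withdrawal of consent, so for other exits the visit schedule and the ITT statements could be read as still applying; section 7.8 also checks admissions to day 28 without excluding those who stopped the liquid. Section 8.7 describes a discussion, so nothing there is automatic. The one mandatory route, 9.7, is the one with no clear link to outcome, and passing 90 ml takes at least seven doses in 24 hours, which nothing suggests would be common. Both liquids contain 70% glucose syrup and no adverse effects are known, so a difference in loss between arms is not shown. The pending SAP could also use the baseline, day-3, day-7 and Early Exit scores in a likelihood-based sensitivity analysis.

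Most of this stands as a limit on size. It does not remove the gap: a person withdrawn from the trial is not naturally read as still attending its contacts, and no section says they are. A model using earlier scores depends on assumptions about the missing day-10 value that collecting the score would make unnecessary.

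Differential loss, though not shown, has possible mechanisms. Investigators and the delivery team are unblinded (7.4), so 8.7 decisions may be made with knowledge of the arm. Colourants are listed only for placebo (8.1), and 7.5 names a new reaction to the colouring as the case in which unblinding might occur, while calling it unlikely.

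A technical objection is that the SE above is unadjusted while the bias uses an ANCOVA slope. If slope 0.5 means a correlation of 0.5, the ANCOVA SE at 86 per arm is 20 × √0.75 × √(2/86) = 2.64, and 1 unit is 0.38 SE rather than 0.33. At 81 per arm the SE is 2.72 and power about 96%. The unadjusted basis is kept because it reproduces the plan's sample size; the conclusion is the same on either.

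**Conclusion.** The concern holds, as a minor one. Followed as written, 9.7 and the stop option in 8.7 take participants out of the trial with no provision for the day-10 score that the ITT analysis needs, unless they leave on day 9 or later.

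The working range for bias is 0 to about 1 unit: zero if loss and gap are equal in the two arms, and 1 unit if one arm loses 5 points more and leavers are 20 units worse with no baseline difference. Exit rates, gap and slope are all assumed. The precision cost is at most small, and the 15% dropout allowance already covers part of it. That allowance protects power; it does not protect against bias. Confidence is medium, because the frequency of such exits is unknown.

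**What to change.** In 8.7, 9.7 and the physician-choice line of 7.10, separate stopping the liquid from withdrawing from the trial:

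- A participant who stops the liquid, or has a confirmed overdose, completes the remaining contacts among days 3, 7, 10, 14 and 28 unless they withdraw consent to follow-up.
- Their day-10 VAS enters the ITT ANCOVA as recorded.
- The Early Exit visit is kept for those who leave follow-up.
- The date and reason for stopping are recorded.

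The clinical decision to stop, the recording of overdose as a deviation and its reporting to the Sponsor are unchanged. The cost is wording in three places, one CRF field, and at most five contacts by phone, text or email for each participant who stops early.

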8.8 Known drug reactions and interaction with other therapies

There are no known drug interactions or adverse effects of Sambucol Original Liquid®. Due to the high sugar content of the liquid participants with unstable diabetes are excluded from the trial.

8.9 Concomitant medication

A record of all concomitant medication will be recorded in the CRF by the Research Nurse during the consent process. If the participant is admitted to Hospital they will be instructed to continue trial treatment to complete the 14 day course.

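### Sections 8.7, 9.7 and 7.10 tie stopping the liquid to leaving the trial, so someone taken off before day 10 can lack the primary VAS and drop out of the ITT analysis

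*Combined protocol and SAP*

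**What the plan says.** Four places describe how a participant may come off the liquid.

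- **8.7 (feeling unwell after a dose).** The participant contacts the research nurse to "discuss whether they should continue or stop treatment and withdraw from the trial". The nurse takes advice from the Chief Investigator.
- **9.7 (overdose).** "In the event of a confirmed overdose the participant will be withdrawn from the trial".
- **7.10 (withdrawal criteria).** The list of reasons for subject withdrawal includes "Responsible physician choice - medical reasons (i.e. individual adverse events or new information gained about a treatment").
- **8.4.7 (recall).** "In the event of a product defect participants will be telephoned and asked to stop taking the product". Withdrawal is not mentioned.

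Section 7.10 goes on to the withdrawal of consent and then says: "No further trial procedures will be undertaken and no data or samples will be collected from the time of withdrawal". The only form it names is the one for consent withdrawal.

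On the analysis side, 10.3.2 and 10.7 specify intention to treat, whatever treatment was actually taken. Section 10.8 omits anyone with a missing value and rules out imputation. Section 7 scores a death as VAS 0.

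On admission to hospital, 8.9 says: "If the participant is admitted to Hospital they will be instructed to continue trial treatment to complete the 14 day course". Section 8.1 describes both liquids as "70% (w/w) of glucose syrup", and 2.1 and 8.8 exclude poorly controlled or unstable diabetes because of the sugar.

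**The concern.** Stopping a treatment and leaving a trial are different events. An ITT analysis needs outcomes from people who stop treatment, and the plan evidently wants poor outcomes to count, since it gives deaths a score. Yet as 8.7 and 9.7 are worded, a research nurse who follows them closes the participant's participation when the liquid stops. The 7.10 list points the same way for a physician's decision. If that happens before day 10 there may be no primary outcome, and 10.8 then removes the person from the ANCOVA. The ITT wording cannot restore a score that was never collected.

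People taken off for medical reasons may well be sicker than the rest of their arm. Losing them unevenly between arms would bias the comparison.

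**Working it through.** **1. The routes off the liquid, side by side**

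| Route | Status in the trial | Is VAS follow-up after stopping stated? |
|---|---|---|
| 8.7, unwell after a dose | Stopping paired with withdrawal | No |
| 9.7, confirmed overdose | Withdrawn | No |
| 7.10, physician's medical decision | Listed as subject withdrawal | No |
| 8.4.7, product recall | Withdrawal not mentioned | No |

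The schedule in 7.7 has an early-exit visit that includes the VAS. That score is taken at exit, and nothing lets it stand in for day 10.

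**2. The plan's own sample size (10.1)**

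Inputs: SD 20, difference 10, 5% significance, 90% power, 15% dropout. Sidedness is not stated. A two-sided two-sample t-test needs 85.03 per group, rounded up to 86, or 172 in total. A one-sided calculation gives 69, which does not match. Dropout: 86/0.85 = 101.2, rounded up to 102 per arm, or 204. The plan's figures are reproduced.

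**3. Power**

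By the normal approximation, power is 94.6% with all 204 day-10 scores, 93.6% with 10 missing and 90.6% with 32 missing (172 left). The allowance of 204 − 172 = 32 covers the loss of information, so the remaining question is bias.

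**4. Bias formula**

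If k of n participants in an arm are omitted and score d units below the rest of that arm, the observed arm mean rises by k × d / n. With n = 102, each omitted person moves the arm mean by 20/102 = 0.20 to 40/102 = 0.39 units for d = 20 to 40. Equal loss with equal d in both arms cancels.

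**5. Illustration for admitted participants**

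The documents give no admission rate, share stopped, timing or VAS gap. Assumed: 2–10% admitted, 25–50% of those stopped, d = 20–40.

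- Stopped per arm: 102 × 2% × 25% = 0.51 to 102 × 10% × 50% = 5.1.
- If stops are spread evenly over 14 days, 9/14 = 64% precede day 10, leaving 0.33 to 3.28 per arm.
- Uneven loss, 10 v 5 admitted with half stopped (5 v 2.5, a net 2.5). All before day 10: 2.5 × 20/102 = 0.49 to 2.5 × 40/102 = 0.98 units. Even timing: net 2.5 × 9/14 = 1.61, giving 1.61 × 20/102 = 0.32 to 1.61 × 40/102 = 0.63 units.
- Extreme: 10% admitted, half stopped, d = 40, all before day 10, loss in one arm only: 5.1 × 40/102 = 2.0 units.

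**6. Scale**

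SE of the difference at 86 per group = 20 × √(2/86) = 3.05. The uneven-loss example is therefore 0.32/3.05 = 0.1 to 0.98/3.05 = 0.3 SE, and the extreme is 2.0/3.05 = 0.66 SE. A shift of one full SE would need a net excess in one arm of 3.05 × 102/40 = 7.8 to 3.05 × 102/20 = 15.6 omitted people.

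**7. Direction**

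If placebo has more admissions and loses more low scores, the benefit of Sambucol is understated. If the Sambucol arm loses more, for instance through 8.7 stops, the same formula overstates it. Both liquids have the same stated glucose syrup content, so sugar-related stops should be similar per admitted participant. Nothing in the documents settles the balance of other stops.

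**The case against.** The strongest reply is that the plan already expects follow-up when treatment is incomplete. The analysis is ITT, missed doses are asked about at the follow-up contacts, compliance is on the schedule throughout, and 7.8 checks admissions and HDU/ITU location over 28 days. Only 8.7 joins stopping and withdrawing in so many words; 7.10 does not say that every medical stop is a withdrawal, and 9.7 concerns overdose alone. This stands in part: a sensible team might well keep calling. But missed doses are not a decision to stop, and no sentence says that someone taken off the liquid stays in the contacts.

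Three stronger readings are tempting and are not supported.

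- *A reader might infer that 7.10 forbids collecting data from anyone taken off the liquid.* The sentence follows directly on consent withdrawal, and the next one refers to consent withdrawal again. That is its most natural scope, although it is not explicitly limited to it.
- *A reader might infer that 8.9 forces a sugary liquid on inpatients against medical judgement, and that this causes the data loss.* Section 8.9 has no exception of its own, but 7.10 gives a physician a medical route off. An instruction to continue does not itself remove a day-10 score.
- *A reader might infer a serious bias, or a damaged HDU/ITU endpoint.* The figures do not show the first, and 7.8 already plans the data for the second.

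It is also fair that someone too ill to swallow the liquid may be too ill to report a VAS. Better wording would not recover every score.

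**Conclusion.** The point holds as a defect of wording with a consequence for the analysis. Sections 8.7 and 9.7, and 7.10 by its list of criteria, link stopping the liquid to leaving the trial. No passage keeps those participants in follow-up, and 10.8 then omits anyone without a day-10 VAS, against the stated ITT principle.

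The expected effect is small: about 0.3 to 1.0 VAS units in the uneven-loss example and 2.0 with every assumption at its extreme, against a target difference of 10 and an SE of about 3. These results rest on assumed rates, timing and VAS gap. They treat every hospital stop before day 10 as an exit, so they are upper figures for admitted participants. They do not count stops under 8.7 and 9.7 outside hospital, so they are not a bound on the whole effect. Neither size nor direction can be fixed from the documents. The sample size is correct and does not change.

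The case for acting rests less on the size of the bias than on delivering the ITT analysis already planned, at almost no cost.

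**What to change.** - In 8.7, 9.7 and 7.10, add: *Stopping the study liquid is not withdrawal from the trial. VAS and admission follow-up, including HDU/ITU, continue to day 28 unless the participant withdraws consent.* Reword 8.7 so that stopping no longer carries withdrawal with it, and 9.7 so that an overdose ends the liquid rather than participation.
- In 7.10, limit the sentence on collecting no further data to withdrawal of consent.
- Record in the CRF the date and reason the liquid was stopped.
- As a secondary safety clarification, align 8.9 with 7.10 by adding: *unless the treating physician or investigator stops it for medical reasons*.

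The cost is wording in four sections and one or two CRF fields. No visits are added, because the contacts on days 3, 7, 10, 14 and 28 and the admission check in 7.8 are already planned. A few admitted participants may take less than the full course, which the ITT analysis accommodates.
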